7.2 Primary Statistical Analyses

7.2.1 Primary analyses

To estimate the sensitivity and specificity of each of the methods of detection, the binomial proportion and its 95% confidence interval will be used. Among participants who are HRA positive for HSIL, McNemar's test will be used to compare routine anal cytology with each of the other methods of detection to determine if sensitivity in the diagnosis of HSIL is improved with the other methods. Similarly, among participants who are HRA negative for HSIL, McNemar's test will be used to compare routine anal cytology with each of the other methods of HPV detection to improve specificity. Positive and negative predictive values will be estimated for each method of detection.

The prevalence of HSIL will be estimated as the proportion of women who are HRA positive for HSIL at entry and its 95% confidence interval. Logistic regression analyses will be used to evaluate the association of potential risk factors (cervical HPV, abnormal cervical cytology, behavioral, and immunologic characteristics, such as plasma HIV-1 RNA, current and nadir CD4 count) with diagnosis of HSIL.

To estimate the incidence of HSIL among women who were HRA negative for HSIL at study entry, the Poisson rate and its 95% confidence interval will be estimated from the number of HSIL cases detected divided by the cumulative years of follow-up across these cases. Behavioral risk factors will be assessed by research staff administered surveys at each study visit. Included in these risk factors is the risk of ongoing sexual exposure to HPV in the study population. Logistic regression will be used to evaluate potential risk factors for incidence of HSIL.

To estimate the incidence of anal HPV among women who were negative for anal HPV at study entry, the Poisson rate and its 95% confidence interval will be estimated from the number of anal HPV cases detected divided by the cumulative years of follow-up across these cases. Logistic regression will be used to evaluate potential risk factors for incidence of anal HPV.

Analysis of the results of the Arbor Vita assay will be delayed after the primary analysis is performed using the results of the Hybrid Capture 2 and Aptima Assays, if the Arbor Vita assay is optimized to yield sufficient results from anal cytology specimens in the future.

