We assure you that your answers will be kept confidential. By providing this information, you will help us a great deal with this study.

Please listen to each question carefully and answer as honestly as possible, even if you only had that type of sexual experience one time. Although some of the behaviors or sexual practices we ask about may be new to you, they are far more common than you may think.

11. Have you ever experienced sexual assault?

| Response | Code |
|-------------------|------|
| Yes | 1 |
| No | 2 |
| I don't know | 98 |
| Decline to answer | 99 |

Sex with Men

The next questions refer only to vaginal sex with men. This is when a man puts his penis, fingers or a sex toy/object in a woman's vagina.

12. Have you ever, any time in your life, had vaginal sex with a man?

| No (skip to question 16) | Yes | Decline to answer (skip to question 16) |
|-----------------------------|-----|--------------------------------------------|
| 0 | 1 | 99 |

13. How many different **men** have you had vaginal sex with **in your entire life**?

| None | 1 | 2-5 | 6-10 | More than 10 | Unsure | Decline to answer |
|------|---|-----|------|--------------|--------|-------------------|
| 0 | 1 | 2 | 3 | 4 | 98 | 99 |

14. How many men have you had vaginal sex with **in the past 6 months**?

| None | 1 | 2-5 | 6-10 | More than 10 | Unsure | Decline to answer |
|------|---|-----|------|--------------|--------|-------------------|
| 0 | 1 | 2 | 3 | 4 | 98 | 99 |

15. How often were condoms used to cover the man's penis, sex toy or object when you had vaginal sex with a man **in the past 6 months**?

| Never | Rarely | Sometimes but less than half | About half the time | More than half the time | Every time | Unsure | Decline to answer |
|-------|--------|------------------------------|---------------------|-------------------------|------------|--------|-------------------|
| 0 | 1 | 2 | 3 | 4 | 5 | 98 | 99 |

Now I am going to ask you questions about anal sex with a man. This is when a man puts his penis, finger, sex toy or object in your anus.

16. Have you **ever**, any time in your life, had anal sex with a man?

| No (skip to question 22) | Yes | Decline to answer (skip to question 22) |
|-----------------------------|-----|--------------------------------------------|
| 0 | 1 | 99 |

17. When was **the last time** a man put his penis in your anus?

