| Within the past week | Within the past month | Within the past 6 months | Within the past year | Over one year ago | Unsure | Decline to answer |
|----------------------|-----------------------|--------------------------|----------------------|-------------------|--------|-------------------|
| 1 | 2 | 3 | 4 | 5 | 98 | 99 |

18. How many different **men** have you had anal sex with **in your entire life**?

| None | 1 | 2-5 | 6-10 | More than 10 | Unsure | Decline to answer |
|------|---|-----|------|--------------|--------|-------------------|
| 0 | 1 | 2 | 3 | 4 | 98 | 99 |

19. How many men have you had anal sex with **in the past 6 months**?

| None | 1 | 2-5 | 6-10 | More than 10 | Unsure | Decline to answer |
|------|---|-----|------|--------------|--------|-------------------|
| 0 | 1 | 2 | 3 | 4 | 98 | 99 |

20. How often did you have anal sex with a man **in the past 6 months**?

| Never | Less than 1 time/month | 1-3 times/month | Once/week | 2-6 times/week | Daily | Unsure | Decline to answer |
|-------|------------------------|-----------------|-----------|----------------|-------|--------|-------------------|
| 0 | 1 | 2 | 3 | 4 | 5 | 98 | 99 |

21. How often was a condom used to cover the man's penis, finger, sex toy or object when you had anal sex with a man **in the past 6 months**?

| Never | Rarely | Sometimes but less than half | About half the time | More than half the time | Every time | Unsure | Decline to answer |
|-------|--------|------------------------------|---------------------|-------------------------|------------|--------|-------------------|
| 0 | 1 | 2 | 3 | 4 | 5 | 98 | 99 |

SEXUALLY TRANSMITTED INFECTIONS

The following questions ask about infections and diseases that are sexually transmitted. Once again, I assure you that your answers will be kept confidential.

Please let us know if you have ever been diagnosed with or treated for any of the infections we ask about now.

22. Have you ever had anal warts? These are **warts** inside or around your anus.

| No | Yes, in the past 6 months | Yes, but longer than 6 months ago | Unsure/Don't know | Decline to answer |
|----|---------------------------|-----------------------------------|-------------------|-------------------|
| 0 | 1 | 2 | 98 | 99 |

23. Have you ever had warts inside your vagina, on the vulva, or in both places?

| No | Inside | Outside | Both | Unsure | Decline to answer |
|----|--------|---------|------|--------|-------------------|

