Contact during sex is an important way in which some women get abnormalities on the cervix and anus. We need your help in understanding how women's behavior can affect their health. For this reason, it is very important for you to answer some questions about your personal sexual behavior. Each question will specify the type of sex to which we refer. Please consider any sexual experiences, even sex that was upsetting or involuntary such as rape.

We assure you that your answers will be kept confidential. By providing this information, you will help us a great deal with this study.

Please listen to each question carefully and answer as honestly as possible, even if you only had that type of sexual experience one time.

8. Have you experienced sexual assault in the past 6 months?

| Response | Code |
|-------------------|-------------|
| Yes | 1 |
| No | 2 |
| I don't know | 98 |
| Decline to answer | 99 |

Sex with Men

The next questions refer only to vaginal sex with men. This is when a man puts his penis, fingers or a sex toy/object in a woman's vagina.

9. Have you had vaginal sex with a man in the past 6 months?

| No (skip to question 12) | Yes | Decline to answer (skip to question 12) |
|------------------------------------|------------|---------------------------------------------------|
| 0 | 1 | 99 |

10. How many men have you had vaginal sex with **in the past 6 months**?

| None | 1 | 2-5 | 6-10 | More than 10 | Unsure | Decline to answer |
|------|---|-----|------|--------------|--------|-------------------|
| 0 | 1 | 2 | 3 | 4 | 98 | 99 |

11. How often were condoms used to cover the man's penis, sex toy or object when you had vaginal sex with a man in the past 6 months?

| Never | Rarely | Sometime s but less than half | About half the time | More than half the time | Every time | Unsure | Decline to answer |
|-------|--------|-------------------------------|---------------------|-------------------------|------------|--------|-------------------|
| 0 | 1 | 2 | 3 | 4 | 5 | 98 | 99 |

Now I am going to ask you questions about anal sex with a man. This is when a man puts his penis, finger, sex toy or object in your anus.

12. Have you had anal sex with a man in the past 6 months?

| No (skip to question 17) | Yes | Decline to answer (skip to question 17) |
|-----------------------------|-----|--------------------------------------------|
| 0 | 1 | 99 |

13. When was the last time a man put his penis in your anus?

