| Within the past week | Within the past month | Within the past 6 months | Unsure | Decline to answer |
|----------------------|-----------------------|--------------------------|--------|-------------------|
| 1 | 2 | 3 | 98 | 99 |

14. How many men have you had anal sex with **in the past 6 months**?

| None | 1 | 2-5 | 6-10 | More than 10 | Unsure | Decline to answer |
|------|---|-----|------|--------------|--------|-------------------|
| 0 | 1 | 2 | 3 | 4 | 98 | 99 |

15. How often did you have anal sex with a man **in the past 6 months**?

| Never | Less than 1 time/month | 1-3 times/month | Once/week | 2-6 times/week | Daily | Unsure | Decline to answer |
|-------|------------------------|-----------------|-----------|----------------|-------|--------|-------------------|
| 0 | 1 | 2 | 3 | 4 | 5 | 98 | 99 |

16. How often was a condom used to cover the man's penis, finger, sex toy or object when you had anal sex with a man **in the past 6 months**?

| Never | Rarely | Sometimes but less than half | About half the time | More than half the time | Every time | Unsure | Decline to answer |
|-------|--------|------------------------------|---------------------|-------------------------|------------|--------|-------------------|
| 0 | 1 | 2 | 3 | 4 | 5 | 98 | 99 |

SEXUALLY TRANSMITTED INFECTIONS

The following questions ask about infections and diseases that are sexually transmitted. Once again, I assure you that your answers will be kept confidential.

Please let us know if, in the past 6 months, you have been diagnosed with or treated for any of the infections we ask about now.

17. Have you had anal warts in the past 6 months? These are **warts** inside or around your anus.

| No | Yes, in the past 6 months | Unsure/Don't know | Decline to answer |
|----|---------------------------|-------------------|-------------------|
| 0 | 1 | 98 | 99 |

18. Have you had warts inside your vagina, on the vulva, or in both places in the past 6 months?

| No | Inside | Outside | Both | Unsure | Decline to answer |
|----|--------|---------|------|--------|-------------------|
| 0 | 1 | 2 | 3 | 98 | 99 |

19. Have you had **herpes** around the vagina or anus in the past 6 months? These are painful blistering sores around your private parts.

| No | Yes, in the past 6 months | Unsure/Don't know | Decline to answer |
|----|---------------------------|-------------------|-------------------|
| 0 | 1 | 98 | 99 |

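### The penile anal-sex recency items (Appendix XIII Q17, Appendix XV Q13) have no 'never' answer after a broad gate question, so lifetime penile exposure cannot be cleanly derived and its associations may be attenuated

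*Combined protocol and SAP*

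**What the plan says.** Appendix XIII places the definition "This is when a man puts his penis, finger, sex toy or object in your anus" before Q16, which asks "Have you ever, any time in your life, had anal sex with a man". No and Decline skip to Q22; Yes leads to Q17. Q17 asks only about the last time a penis was involved. Its options are five dated periods, Unsure and Decline, and the list ends "Within the past year | Over one year ago | Unsure | Decline to answer".

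The next items return to the broad definition. Q18 asks "How many different men have you had anal sex with in your entire life", Q19 and Q20 ask about recent partners and frequency, and Q21 pools all kinds of contact by name: "How often was a condom used to cover the man's penis, finger, sex toy or object when you had anal sex with a man".

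Appendix XV repeats the pattern at Q12-16 for the past 6 months. Q13 asks "When was the last time a man put his penis in your anus" and offers only "Within the past week | Within the past month | Within the past 6 months | Unsure | Decline to answer".

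Section 7.2.1 enters behavioral factors in logistic models. In the incident-HSIL paragraph it adds: "Included in these risk factors is the risk of ongoing sexual exposure to HPV in the study population". It does not say which questionnaire items define that exposure. Objectives 2.2.2 and 2.2.3 refer to risk factors in general, and hypothesis 2.1.2 refers to behavioral characteristics.

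**The concern.** The gate question and the item behind it cover different populations. A woman with finger, toy or object contact only passes the gate truthfully and then meets a question with no true answer for her. Her record will show either penile contact that did not happen or a missing code. The baseline form does have a not-applicable code on other items (Q8-10, for example), so the gap at Q17 looks like an oversight.

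Risk factors for prevalent and incident HSIL, and for incident anal HPV, are primary objectives. If non-penile contact carries less HPV risk, counting it as penile exposure would be expected to pull the odds ratio toward 1, provided the error is unrelated to outcome. Cases are few: Section 7.1 implies 300 × 0.10 = 30 prevalent cases. Its two incidence scenarios give 2.06/100 × 486 ≈ 10 and 3.09/100 × 486 ≈ 15 incident cases.

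**Working it through.** **Step 1. What each answer can support.** The plan states no effect size or power for anal sex, so there is no planned figure to reproduce. The check starts from the forms.

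| Measure | Source | Derivable? |
|---|---|---|
| Penile anal sex in the past year, baseline | Q17 codes 1-4 | Largely, if answers are valid |
| Penile anal sex in the past 6 months, follow-up | Q13 codes 1-3 | Largely, if answers are valid; there is no older period to absorb a misfit |
| Lifetime ever/never penile | Q16 with Q17 | No: code 5 mixes true past exposure with women who have no valid answer; others fall into 98, 99 or blank |
| Penile partners, frequency, condom use | Q18-21, follow-up Q14-16 | No: all use the broad definition |

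**Step 2. How much attenuation is possible.** From Section 7.1: N = 300 and HSIL prevalence 10%. Assumed, because the documents give no figures: penile share p = 0.30, true odds ratio 2.5, no excess risk from other contact, and an analysis of the broad Q16 variable alone. Let s be the share of all women with non-penile contact only.

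Baseline risk r0 and penile risk r1 satisfy p·r1 + (1 − p)·r0 = 0.10 and odds(r1) = 2.5 × odds(r0). The solution is r0 = 0.0727 and r1 = 0.1638. Check: 0.30 × 0.1638 + 0.70 × 0.0727 = 0.100.

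Risk in the pooled exposed group is rE = (p·r1 + s·r0)/(p + s), and the expected odds ratio is odds(rE)/odds(r0), with odds(r0) = 0.0784.

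- s = 0.03: rE = (0.0491 + 0.0022)/0.33 = 0.1555, odds 0.1841, odds ratio 2.35.
- s = 0.20: rE = (0.0491 + 0.0145)/0.50 = 0.1273, odds 0.1459, odds ratio 1.86.

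Power is the normal approximation for two proportions (two-sided 0.05, N = 300, pooled variance under the null).

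| Non-penile only (s) | Expected odds ratio | Power |
|---|---|---|
| 0 (no error) | 2.50 | 0.65 |
| 3% | 2.35 | 0.60 |
| 5% | 2.27 | 0.57 |
| 10% | 2.10 | 0.49 |
| 20% | 1.86 | 0.35 |

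With p = 0.40, the odds ratio is 2.18 at s = 10% and 1.97 at s = 20%.

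**Step 3. What Q17 recovers.** If s = 10% but half of those women are kept out of the exposed group through Q17, the misplaced share is 5%. The result is then the 5% row: odds ratio 2.27, power 0.57. If other contact itself carries an odds ratio of 1.5, pooling 10% gives 2.24.

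**The case against.** A reader might infer that penile anal sex cannot be separated at all and that its association is therefore diluted. The documents do not support either statement. Q17 and Q13 name the penis, so their recent codes fail only when a woman affirmatively reports recent contact that did not occur. Research staff administer the forms (Section 4.3.5), so a woman can say that the question does not apply and the item can be left blank or coded as missing. At baseline the contamination should fall mainly in code 5 and the missing codes. The follow-up form is somewhat more exposed, because Q13 has no older period.

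Nor do the documents name penile anal sex as an exposure. The objectives say only risk factors, and the sentence on ongoing sexual exposure appears once, under incident HSIL. The broad definition parallels the one for vaginal sex on the same form and may be deliberate. That is a reason to keep the broad variable; it does not give the affected women a true answer at Q17.

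The larger attenuation figures assume that Q16 alone is analysed, which Section 7.2.1 does not say, and that 10-20% of women had non-penile contact only. At 3-5% the loss is modest. Power is only 0.65 even with a perfect item, so the small number of cases limits this analysis more than the wording does.

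What stands is the missing answer on both forms, the loss of lifetime penile status, and the pooled partner, frequency and condom items.

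**Conclusion.** The form defect is real and occurs in both questionnaires. It leaves lifetime penile status uncertain and the partner, frequency and condom items unspecific; recent penile exposure largely survives. Associations with HSIL and anal HPV may be attenuated. That they are attenuated is not shown. The direction rests on error unrelated to outcome and lower risk from other contact, and the documents give no data on either. Under the stated assumptions an odds ratio of 2.5 would appear as anything from about 2.35 to 1.86 if Q16 alone were used, and would be closer to 2.5 with Q17. Objectives 2.2.2 and 2.2.3 are affected; the sensitivity and specificity objective (2.2.1) is not. This is a small correction, worth making because it costs little.

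**What to change.** 1. Prospectively add a response such as 'Never with a penis (finger, toy or object only)' to Appendix XIII Q17, and 'Not with a penis in the past 6 months' to Appendix XV Q13.
2. In Section 7.2.1, define penile anal sex from Q17 and Q13 and report it alongside the broad variable from Q16 and Q12.
3. Describe Q18-21 and follow-up Q14-16 as measures of broad anal contact. Routing non-penile women past them would not make them penile-specific, because women with both kinds of contact would still give pooled answers.
4. Do not re-ask only the women who continue. Under Section 5.1, women with histologic HSIL at enrollment leave, so the correction would reach non-cases but not prevalent cases and make the error differential by outcome. Instead, treat earlier Q17 answers coded 5, 98 or 99 as uncertain in a sensitivity analysis.

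The cost is one response code per form with the matching data field. Baseline answers already collected stay uncorrected.

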32. ANAL PAP SMEAR

An anal Pap smear will be taken. This is like a cervical Pap smear. A Q-tip type swab will be inserted into the anus by the doctor or nurse practitioner to obtain cells that will be sent to the laboratory to check for abnormalities.

| Statement | Strongly disagree | Slightly disagree | Neutral | Slightly agree | Strongly agree | Decline to answer |
|-----------------------------------------------|-----------------------------|-----------------------------|---------|-------------------|-------------------|----------------------|
| I am concerned about pain. | 1 | 2 | 3 | 4 | 5 | 99 |
| I feel the exam will be uncomfortable. | 1 | 2 | 3 | 4 | 5 | 99 |
| I feel at ease. | 1 | 2 | 3 | 4 | 5 | 99 |
| I am prepared to have the procedure. | 1 | 2 | 3 | 4 | 5 | 99 |

33. HIGH RESOLUTION ANOSCOPY

High resolution anoscopy is done with use of a plastic tube instrument inserted in the anus to look at the tissue under a special light to see if there are warts or other abnormalities in the anal area. Vinegar is used to make any abnormal areas show up better under the light.

Any abnormalities seen will be biopsied, or removed, with a small cutting instrument to send to the laboratory for special analysis.

| Statement | Strongly disagree | Slightly disagree | Neutral | Slightly agree | Strongly agree | Decline to answer |
|-----------------------------------------------|-----------------------------|-----------------------------|---------|-------------------|-------------------|----------------------|
| I am concerned about pain. | 1 | 2 | 3 | 4 | 5 | 99 |
| I feel the exam will be uncomfortable. | 1 | 2 | 3 | 4 | 5 | 99 |
| I feel at ease. | 1 | 2 | 3 | 4 | 5 | 99 |
| I am prepared to have the procedure. | 1 | 2 | 3 | 4 | 5 | 99 |

34. Which of the following examinations or procedures concerns you the **very most** today? (Choose one)

| Code | Procedure |
|------|--------------------------|
| 0 | No Concern |
| 1 | Anal Pap smear |
| 2 | High resolution anoscopy |
| 3 | Possible biopsy |
| 99 | Decline to answer |

HEALTH BEHAVIOR QUESTIONS

Now I am going to ask you a few questions about yourself.

[from ACTG self report, questions E, H, QL0742(A5257)/ 12-31-08]

35. Are you on HIV medication(s)?

| No (skip to question 37) | Yes | Unsure/Don't know (skip to question 37) |
|-----------------------------|-----|--------------------------------------------|
| 0 | 1 | 98 |

36. Rate your **ability** to take all of your HIV medications as specifically prescribed.

| Very poor | Poor | Fair | Good | Very good | Excellent | N/A | Unsure/Don't know | Decline to answer |
|-----------|------|------|------|-----------|-----------|-----|-------------------|-------------------|
| 1 | 2 | 3 | 4 | 5 | 6 | 97 | 98 | 99 |

SMOKING QUESTIONS

37. Altogether, have you smoked at least 100 or more cigarettes in your entire lifetime?

INTERVIEWER NOTE: IF NECESSARY: 5 packs = 100 cigarettes

| No (skip to question 40) | Yes | Unsure/Don't know (skip to question 40) | Decline to answer |
|-----------------------------|-----|--------------------------------------------|-------------------|
| 0 | 1 | 98 | 99 |

Ask former and current smokers the following questions:

38. When you were smoking most heavily, how many cigarettes did you smoke on an average day? (1 pack = 20 cigarettes)

_____ Cigarettes per day

39. For how long did you smoke this heavily? (If time unit is known, indicate the number of years.)

| Code | Years |
|------|---------|
| 98 | Unknown |

COST/TRANSPORTATION QUESTIONS

40. What is the main source of your financial support, including food, rent, and other expenses?
 (Check participant's response. If more than one choice given, PROBE: Is one of these the most important source of your income? If participant answers "No," record all responses given)

| Response | Code |
|-----------------------------------------------------------------|------|
| Own job or salary. | 1 |
| Someone else's job or salary (Specify relationship): _____) | 2 |
| Public assistance, e.g., AFDC, SSI, food stamps | 3 |
| Other (Specify): _____) | 8 |
| Unknown | 98 |

41. Which one best describes your hourly wage or annual income?

| Hourly Wage | Annual Income |
|------------------------|--------------------------|
| \$0.00 - \$4.99 | \$0.00 - \$9,999 |
| \$5.00 - \$7.25 | \$10,000 - \$14,999 |
| \$7.26 - \$9.99 | \$15,000 - \$19,999 |
| \$10.00 - \$14.99 | \$20,000 - \$29,999 |
| \$15.00 - \$19.99 | \$30,000 - \$39,999 |
| \$20.00 - \$24.99 | \$40,000 - \$49,999 |
| \$25.00 - \$29.99 | \$50,000 - \$59,999 |
| \$30.00 - \$34.99 | \$60,000 - \$69,999 |
| \$35.00 - \$39.99 | \$70,000 - \$79,999 |
| \$40.00 - \$49.99 | \$80,000 - \$99,999 |
| More than \$50.00/hour | More than \$100,000/year |

42. Did you miss work today for this visit?

| No | Yes | Not applicable/Don't Work |
|----|-----|---------------------------|
| 0 | 1 | 99 |

43. How did you get to the clinic today?

| Response | Code |
|----------------------------------------------------------------|------|
| Drive yourself | 1 |
| Get a ride from someone else in a personal vehicle | 2 |
| Take public transportation such as the metro bus or metro rail | 3 |
| Take a taxi | 4 |
| Walk or ride bike, or | 5 |
| Get there some other way (SPECIFY) _____ | 6 |
| Decline to answer | 99 |

44. If you took private/public transportation, what was the fare? \$ _____

45. How much time (including travelling time) will you miss from your usual activities because of this appointment?

| Response | Code |
|-------------------------------------------|------|
| Less than 15 minutes | 1 |
| 15 to 30 Minutes | 2 |
| 31 Minutes to 60 Minutes (1 Hour) | 3 |
| 61 Minutes to 90 Minutes | 4 |
| 91 Minutes to 120 Minutes (2 Hours) | 5 |
| 120 Minutes to 180 Minutes (2 to 3 Hours) | 6 |
| 180 Minutes to 240 Minutes (3 to 4 Hours) | 7 |
| 240 Minutes to 300 Minutes (4 to 5 Hours) | 8 |
| 300 Minutes to 360 Minutes (5 to 6 Hours) | 9 |
| More than 360 Minutes (More than 6 Hours) | 10 |

46. How far did you travel for this appointment? _____ miles

47. If you drove, how much do you expect to pay for the parking? \$ _____

| |
|----|
| NA |
| 99 |

48. If you are accompanied to your appointment by someone who missed work, what is the gender and age of this person?

| Accompanied | | | Not accompanied |
|-------------|--------|-----|--------------------|
| Male | Female | Age | 0 |
| 1 | 2 | | |

49. Did you have to get a caretaker today to attend to your children and/or an adult person living in your household in order to come to your appointment?

| No (Skip to question number 53) | Yes |
|------------------------------------|-----|
| 0 | 1 |

50. How much do you expect to pay the caretaker for today? (If no payment, skip to question 51)

\$ _____

51. Did the caretaker miss work in order to help you?

| No (Skip to question number 52) | Yes |
|------------------------------------|-----|
| 0 | 1 |

52. What is the gender and age of the caretaker?

| Male | Female | Age |
|------|--------|-----|
| 1 | 2 | |

DEMOGRAPHIC QUESTIONS

53. What is your marital status?

| Response | Code |
|----------------------------------|------|
| Married | 1 |
| Not married, living with someone | 2 |
| Divorced/separated | 3 |
| Widowed | 4 |
| Single/never married | 5 |
| Other: (specify) _____ | 6 |
| Decline to answer | 99 |

54. What is your country of origin (where were you born)?

| Response | Code |
|-------------------------------------|------|
| United States of America | 1 |
| United States territory—Puerto Rico | 2 |

| | |
|-------------------------------|----|
| Haiti | 3 |
| Cape Verde | 4 |
| Uganda | 5 |
| Nigeria | 6 |
| Cameroon | 7 |
| Kenya | 8 |
| Mexico | 9 |
| Other Latin America (specify) | 10 |
| Other Africa (specify) | 11 |
| Other: (specify) | 99 |

55. If you were born outside the United States, what age were you when you first came to live in the United States?

| Enter Age in Years | N/A | Unsure/Don't know | Decline to answer |
|--------------------|-----|-------------------|-------------------|
| | 97 | 98 | 99 |

56. What is the last grade (highest level) of school that you completed?

| Grade | Code |
|-----------------------------------|------|
| 8 th grade or less | 1 |
| Some high school | 2 |
| High school diploma | 3 |
| Some college or vocational school | 4 |
| Associate degree | 5 |
| College (4 year) degree | 6 |
| Graduate or professional degree | 7 |
| Don't know | 98 |
| Decline to answer | 99 |

**APPENDIX XIV: POST-PROCEDURE TELEPHONE FOLLOW-UP QUESTIONNAIRE
AND SCRIPT**

**Screening HIV-Infected Women for Anal Cancer Precursors
POST PROCEDURE QUESTIONS**

The following questions will be asked **2-5 weeks** after the procedures have been completed via a telephone follow up call, or a visit if preferred by the participant and/or investigator.

Participant ID: 084 - _____ - _____

Date of administration: _____ / _____ / _____

Administered by: _____

Location of administration (e.g. clinic or telephone): _____

Date of last study procedure visit: _____ / _____ / _____

Thank you for agreeing to speak with me today.

I will be asking some personal questions. Most of them are the same or similar to the original questions you answered previously. Again, if you feel uncomfortable answering any question or want to stop at any time, just let me know.

POST PROCEDURE QUESTIONS

1. Did you have bleeding following the last HRA procedure? (If No, skip to question 4.)

| Response | Code |
|----------|------|
| Yes | 1 |
| No | 2 |

2. How many days did you have bleeding? _____ days

3. Did you feel the bleeding was:

| Response | Code |
|----------|------|
| Mild | 1 |
| Moderate | 2 |
| Severe | 3 |

4. Did you have pain following the last HRA procedure? (If No, skip to question 9.)

| Response | Code |
|----------|------|
| Yes | 1 |
| No | 2 |

5. How many days after the HRA procedure did you have pain? _____ days

6. Did you feel the pain was:

| Response | Code |
|----------|------|
| Mild | 1 |
| Moderate | 2 |
| Severe | 3 |

7. Did you take any medication for the pain? (If no, skip to question 9.)

| Response | Code |
|----------|------|
| Yes | 1 |
| No | 2 |

8. And if so, what medication(s)

| Response | Code |
|---------------|------|
| Acetaminophen | 1 |
| NSAIDS | 2 |
| Narcotics | 3 |

9. Did you miss work because of bleeding or pain? (If no, skip to question 12.)

| Response | Code |
|----------|------|
| Yes | 1 |
| No | 2 |

10. If yes, was it because of the:

| Response | Code |
|----------|------|
| Bleeding | 1 |
| Pain | 2 |
| Both | 3 |

11. How many days did you miss work due to either bleeding or pain? _____ days

12. Did you have any unscheduled visits to any healthcare provider because of bleeding or pain after the HRA?

| Response | Code |
|----------|------|
| Yes | 1 |
| No | 2 |

13. How many times have you had high resolution anoscopy (HRA)? (If only one time, skip to question 15.)

| Response | Code |
|--------------|------|
| 1 time | 1 |
| 2-4 times | 2 |
| 5-10 times | 3 |
| More than 10 | 4 |

14. Comparing your experience with the first (or former) procedure to this most recent procedure, would you say that the most recent procedure was:

| Response | Code |
|--------------|------|
| Better | 1 |
| Same | 2 |
| Worse | 3 |
| I don't know | 98 |

15. Before your recent HRA procedure, how informed were you about the purpose of HRA in screening for anal cancer?

| Response | Code |
|-------------------|------|
| Well informed | 1 |
| Somewhat informed | 2 |
| Poorly informed | 3 |
| I don't know | 98 |

16. Before your recent HRA procedure, how informed were you about any discomfort that you could experience during the procedure?

| Response | Code |
|-------------------|------|
| Well informed | 1 |
| Somewhat informed | 2 |
| Poorly informed | 3 |
| I don't know | 98 |

17. Before your recent HRA procedure, how informed were you about any discomfort/bleeding you might have after the procedure?

| Response | Code |
|-------------------|------|
| Well informed | 1 |
| Somewhat informed | 2 |
| Poorly informed | 3 |
| I don't know | 98 |

18. Before your recent HRA procedure, how informed were you about self-care at home after the procedure?

| Response | Code |
|-------------------|------|
| Well informed | 1 |
| Somewhat informed | 2 |
| Poorly informed | 3 |
| I don't know | 98 |

19. During your recent HRA procedure did you feel supported and well-cared for by the providers who performed the HRA?

| Response | Code |
|--------------|------|
| Yes | 1 |
| No | 2 |
| I don't know | 98 |

20. Some people who have experienced sexual abuse, rape, or other trauma in their lives find the HRA procedure particularly distressing. Have you have had an experience such as these in your lifetime? (IF NO, go to question 22).

| Response | Code |
|--------------|------|
| Yes | 1 |
| No | 2 |
| I don't know | 98 |

21. IF YES, did your most recent HRA procedure cause you to remember the trauma?

| Response | Code |
|----------------|------|
| Yes | 1 |
| No | 2 |
| Not applicable | 97 |
| I don't know | 98 |

22. During your recent HRA procedure did you feel your privacy was respected?

| Response | Code |
|--------------|------|
| Yes | 1 |
| No | 2 |
| I don't know | 98 |

23. How likely would you be to follow recommendations to repeat the HRA procedures?

| Response | Code |
|-------------------|------|
| Very unlikely | 1 |
| Somewhat unlikely | 2 |
| Neutral | 3 |
| Somewhat likely | 4 |
| Very likely | 5 |
| I don't know | 98 |

Please tell me your experience with each of the examinations or procedures. For each of these statements, please tell me whether you **agree** or **disagree**. Then you will be asked if you slightly or strongly agree/disagree with the statement.

24. Anal Pap smear

| Statement | Strongly disagree | Slightly disagree | Neutral | Slightly agree | Strongly agree | Decline to answer |
|-----------------------------------------------------------|-----------------------------|-----------------------------|---------|-------------------|-------------------|----------------------|
| I felt pain during the procedure. | 1 | 2 | 3 | 4 | 5 | 99 |
| I felt uncomfortab le during the exam. | 1 | 2 | 3 | 4 | 5 | 99 |
| I felt at ease. | 1 | 2 | 3 | 4 | 5 | 99 |
| I was prepared to have the procedure. | 1 | 2 | 3 | 4 | 5 | 99 |

25. High resolution anoscopy

| Statement | Strongly disagree | Slightly disagree | Neutral | Slightly agree | Strongly agree | Decline to answer |
|-----------------------------------------------------------|-----------------------------|-----------------------------|---------|-------------------|-------------------|----------------------|
| I felt pain during the procedure. | 1 | 2 | 3 | 4 | 5 | 99 |
| I felt uncomfortab le during the exam. | 1 | 2 | 3 | 4 | 5 | 99 |
| I felt at ease. | 1 | 2 | 3 | 4 | 5 | 99 |
| I was prepared to have the procedure. | 1 | 2 | 3 | 4 | 5 | 99 |

26. Is there anything that will make getting the exam procedures the next time more comfortable for you?

| Response | Code |
|-----------------------------|------|
| Yes | 1 |
| No (Questionnaire complete) | 2 |
| I don't know | 98 |

27. Would any of the following make the next HRA procedure more comfortable for you?

| Response | Yes | No |
|--------------------------------------------------------------------|-----|----|
| More explanation about what to expect from a health care provider. | 1 | 2 |
| Medication to calm my nerves. | 1 | 2 |
| More effective pain medication. | 1 | 2 |
| Medication that will make me sleep during the procedure. | 1 | 2 |

28. If above answers were all no, but you feel there is something that would make the procedures more comfortable for you, please tell me what that would be:

****AFTER COMPLETING QUESTIONNAIRE, PROVIDE THE PARTICIPANT THE RESULTS FROM HER PAP TESTS AND ANY BIOPSIES TAKEN, AND REVIEW ANY RECOMMENDATIONS FOR FOLLOW-UP.****

